## **5 SOFTWARE DOCUMENTATION**

All summaries and statistical analyses will be generated using SAS version 9.0 or higher.

## 7 LIST OF APPENDICES

- [Appendix A:](#) Criteria for potentially clinically significant abnormalities for studies in children
- [Appendix B:](#) Visit windows based on day ranges for laboratory values, vital Signs, ADA, and PK measurements
- [Appendix C:](#) Mock up tables for safety events and efficacy endpoints before and after dose adjustment

## Appendix A Criteria for Potentially Clinically Significant Abnormalities for Studies in Children

CRITERIA for POTENTIALLY CLINICALLY SIGNIFICANT ABNORMALITIES For Studies in Children			
Parameter	Age range	PCSA	Comments
ECG parameters			Ref. : Rijnbeek P.R. et al., Eur Heart J 2001; Davignon A. et al., Ped Cardiol 1979/1980; Semizel E. et al., Cardiol Young 2008; Mulberg AE et al. Pediatric Drug Development Concepts and applications. John Wiley & sons, Inc. 2009
HR	Birth/0 to 27 days old (Neonates)	≤90 bpm and decrease from baseline ≥20 bpm ≥190 bpm and increase from baseline ≥20 bpm	
	28 days/1 month to 23 months old (Infants)	≤80 bpm and decrease from baseline ≥20 bpm ≥175 bpm and increase from baseline ≥20 bpm	
HR	24 months/2 years to <6 years old (Children)	≤75 bpm and decrease from baseline ≥20 bpm ≥140 bpm and increase from baseline ≥20 bpm	
	6 to <12 years old (Children)	≤50 bpm and decrease from baseline ≥20 bpm ≥120 bpm and increase from baseline ≥20 bpm	
HR	12 to 16/18 years old (Adolescents)	≤50 bpm and decrease from baseline ≥20 bpm ≥120 bpm and increase from baseline ≥20 bpm	
	PR	Birth/0 to 27 days old (Neonates)	
PR	28 days/1 month to 23 months old (Infants)	≥140 ms	
	24 months/2 years to <6 years old (Children)	≥160 ms	
PR	6 to <12 years old (Children)	≥170 ms	
	12 to 16/18 years old (Adolescents)	≥180 ms	
QRS	Birth/0 to 27 days old (Neonates)	≥85 ms	
	28 days/1 month to 23 months old (Infants)	≥85 ms	
QRS	2 to <6 years old (Children)	≥95 ms	
	6 to <12 years old (Children)	≥100 ms	
QRS	12 to 16/18 years old (Adolescents)	≥110 ms	

**CRITERIA for POTENTIALLY CLINICALLY SIGNIFICANT ABNORMALITIES  
 For Studies in Children**

Parameter	Age range	PCSA	Comments
QTc	Birth/0 to <12 years old (Neonates, Infants, Children)	Absolute values (ms) Borderline: 431-450 ms Prolonged*: >450 ms Additional: ≥500 ms	To be applied to QTcF  *QTc prolonged and ΔQTc>60 ms are the PCSA to be identified in individual subjects/patients listings.
		AND	
		Increase from baseline Borderline: Increase from baseline 30-60 ms Prolonged*: Increase from baseline >60 ms	
	12 to 16/18 years old (Adolescents)	Borderline: 431-450 ms (Boys); 451-470 ms (Girls) Prolonged*: >450 ms (Boys); >470 ms (Girls) Additional: ≥500 ms	
		AND	
		Increase from baseline Borderline: Increase from baseline 30-60 ms Prolonged*: Increase from baseline >60 ms	
Vital Signs			Ref. : Kidney Disease Outcomes Quality Initiatives (KDOQI) Guideline 13; 1996; The fourth report on the diagnosis, evaluation, and treatment of high blood pressure in children and adolescents, Pediatrics 2004; Bowman E & Fraser S Neonatal Handbook 2012; Mulberg AE et al. Pediatric Drug Development Concepts and applications. John Wiley & sons, Inc. 2009; Pediatric respiratory rates http://www.health.ny.gov/
SBP	Birth/0 to 27 days old (Neonates)	≤60 mmHg and decrease from baseline ≥20 mmHg ≥85mmHg and increase from baseline ≥20 mmHg	Based on definition of Hypertension as average SBP or DBP ≥ 95 th percentile for gender, age, and height on ≥ 3 occasions
	28 days/1 month to 23 months old (Infants)	≤70 mmHg and decrease from baseline ≥20 mmHg ≥98 mmHg and increase from baseline ≥20 mmHg	
	24 months/2 years to <6	≤70 mmHg and decrease from baseline ≥20	

**CRITERIA for POTENTIALLY CLINICALLY SIGNIFICANT ABNORMALITIES  
For Studies in Children**

Parameter	Age range	PCSA	Comments
	years old (Children)	mmHg ≥101mmHg and increase from baseline ≥20 mmHg	
	6 to <12 years old (Children)	≤80 mmHg and decrease from baseline ≥20 mmHg ≥108 mmHg and increase from baseline ≥20 mmHg	
	12 to 16/18 years old (Adolescents)	≤90 mmHg and decrease from baseline ≥20 mmHg ≥119mmHg and increase from baseline ≥20 mmHg	
DBP	Birth/0 to 27 days old (Neonates)	≤34 mmHg and decrease from baseline ≥10 mmHg ≥50mmHg and increase from baseline ≥10 mmHg	
	28 days/1 month to 23 months old (Infants)	≤34 mmHg and decrease from baseline ≥10 mmHg ≥54mmHg and increase from baseline ≥10 mmHg	
	24 months/2 years to <6 years old (Children)	≤34 mmHg and decrease from baseline ≥10 mmHg ≥59mmHg and increase from baseline ≥10 mmHg	
	6 to <12 years old (Children)	≤48 mmHg and decrease from baseline ≥10 mmHg ≥72mmHg and increase from baseline ≥10 mmHg	
	12 to 16/18 years old (Adolescents)	≤54 mmHg and decrease from baseline ≥10 mmHg ≥78mmHg and increase from baseline ≥10 mmHg	
Orthostatic hypotension	All age ranges	SBP : St — Su ≤ - 20 mmHg DBP : St — Su ≤ - 10 mmHg	
Temperature	All age ranges	Rectal, ear or temporal artery: ≥100.4 °F/38.0 °C Oral or pacifier: ≥99.5 °F/37.5 °C Axillary or skin infrared: ≥99 °F/37.2 °C	Ear temperature not accurate below 6 months of age
Respiratory rate	Birth/0 to 27 days old (Neonates)	< 30 per minutes > 60 per minutes	Based on normal range
	28 days/1 month to 23 months old (Infants)	< 24 per minutes > 40 per minutes	
	24 months/2 years to <6 years old (Children)	< 22 per minutes > 34 per minutes	
	6 to <12 years old (Children)	< 18 per minutes > 30 per minutes	
	12 to 16/18 years old (Adolescents)	< 12 per minutes > 20 per minutes	
SaO2	All age ranges	≤95 %	
Weight	All ranges	≥5 % weight loss from baseline	Based on identification of trends in the child's growth with a series of visits WHO Multicentre Reference

**CRITERIA for POTENTIALLY CLINICALLY SIGNIFICANT ABNORMALITIES  
For Studies in Children**

Parameter	Age range	PCSA	Comments
			Study Group, 2006; Center for Disease Control. Growth chart 2007
Clinical Chemistry			Ref Molleston JP et al. JPGN 2011; Moritz et al., Pediatrics 1999; Moritz et al., Pediatr Nephrol 2005 ; Sedlacek et al., Seminars in Dialysis 2006) Gong G et al. Clinical Biochemistry 2009; Masilamani et al. Arch Dis Children 2012; Mulberg AE et al. Pediatric Drug Development Concepts and applications. John Wiley & sons, Inc. 2009
ALT/SGPT	All age ranges	$\geq 3$ ULN By distribution analysis: $\geq 3$ ULN $\geq 5$ ULN $\geq 10$ ULN $\geq 20$ ULN	Based on normal ranges: 6 to 50 U/L (0-5 days), 5 to 45 U/L (1-19 years)
AST/SGOT	All age ranges	$\geq 3$ ULN By distribution analysis: $\geq 3$ ULN $\geq 5$ ULN $\geq 10$ ULN $\geq 20$ ULN	Based on normal ranges: 35 to 140 U/L (0-5 days), 15 to 55 U/L (1-9 years), 5 to 45 U/L (10-19 years)
Alkaline Phosphatase	All age ranges	$\geq 1.5$ ULN	Based on normal ranges: 145 to 420 U/L (1-9 years), 130 to 560 U/L (10-11 years), 200 to 495 U/L (Boys 12-13 years), 105 to 420 U/L (Girls 12-13 years), 130 to 525 U/L (Boys 14-15 years), 70 to 130 U/L (Girls 14-15 years), 65 to 260 U/L (Boys 16-19 years), 50 to 130 U/L (Girls 16-19 years)
Total Bilirubin	All age ranges	$\geq 1.3$ ULN	CF = mg x 1.7 = $\mu$ mol Based on normal ranges: <6 mg/dL (Term 0-1 day), <8 mg/dL (Term 1-2 days), <12 mg/dL (Term 3-5 days), <1

**CRITERIA for POTENTIALLY CLINICALLY SIGNIFICANT ABNORMALITIES  
For Studies in Children**

Parameter	Age range	PCSA	Comments
			mg/dL (Term >5 days)
Conjugated Bilirubin	All age ranges	>35% Total Bilirubin and TBILI ≥ 1.3 ULN	CF = mg x 1.7 = μmol Based on normal range: 0 to 0.4 mg/dL
ALT and Total Bilirubin	All age ranges	ALT ≥ 3 ULN and Total Bilirubin ≥ 2 ULN	
CPK	All age ranges	≥ 3 ULN	
Creatinine	Birth/0 to <6 years old (Neonates, Infants, Children)	>53 μmol/L or 0.6 mg/dL	CF = mg x 8.8 = μmol
	6 years to <12 years old (Children)	≥ 90 μmol/L or 1.1 mg/dL	Based on normal ranges: ≤ 0.6 mg/dL (0-1 year), 0.5 to 1.5 mg/dL (1 to 16/18 years)
	12 years to 16/18 years old (Adolescents)	≥ 132 μmol/L or 1.5 mg/dL	
Creatinine Clearance	All age ranges	50 % of normal < 60 ml/min/1.73m  (After 1 year old)	Based on GFR Bedside Schwartz Formula  Based on normal ranges: 20 to 50 (<8 days), 25 to 80 (8 days to 1 month), 30 to 90 (1-6 months), 40 to 115 (6-12 months), 60 to 190 (12-23 months), 90 to 165 (2-12 years), 80-120 (After 12 years)
Uric Acid	All age ranges	≤ 2.0 mg/dL or 119 μmol/L ≥ 8.0 mg/dL or 476 μmol/L	CF = mg x 5.95 = μmol Based on normal ranges: 2.4 to 6.4 mg/dL
Blood Urea Nitrogen (BUN)	Birth/0 to 27 days old (Neonates)	≥ 4.3 mmol/L or 12 mg/dl	CF = g x 16.66 = mmol
	28 days/1 month to 16/18 years old (Infants, Children, Adolescents)	≥ 6.4 mmol/L or 18 mg/dl	Based on normal ranges: 3 to 12 mg/dL (NN); 5 to 18 mg/dL (other classes of age)
Chloride	All age ranges	≤ 80 mmol/L or 80 mEq/L ≥ 115 mmol/L or 115 mEq/L	CF = 1  Based on normal range: 98 to 106
Sodium	All age ranges	≤ 129 mmol/L or 129 mEq/L ≥ 150 mmol/L or 150 mEq/L	CF = 1

**CRITERIA for POTENTIALLY CLINICALLY SIGNIFICANT ABNORMALITIES  
For Studies in Children**

Parameter	Age range	PCSA	Comments
			Based on normal range : 134 to 146
Potassium	Birth/0 to 27 days old (Neonates)	≤3.0 mmol/L or 3.0 mEq/L ≥7.0 mmol/L or 7.0 mEq/L	CF = 1 Based on normal ranges: 3.0 to 7.0 (NN); 3.5 to 6.0 (Infants); 3.5 to 5.0 (>Infants)
	28 days/1 month to 23 months old (Infants)	≤3.5 mmol/L or 3.5 mEq/L ≥6.0 mmol/L or 6.0 mEq/L	
	24 months/2 years to 16/18 years old (Children, Adolescents)	≤3.5 mmol/L or 3.5 mEq/L ≥5.5 mmol/L or 5.5 mEq/L	
Bicarbonate	All age ranges	≤16 mmol/L or 16 mEq/L ≥30 mmol/L or 30 mEq/L	CF = 1 Based on normal range: 18 to 26
Calcium total	All age ranges	≤2.0 mmol/L or 8.0 mg/dL ≥2.9 mmol/L or 11.6 mg/dL	CF = mg x 0.025 = mmol Based on normal range: 8.4 to 10.9 mg/dL
Calcium ionized	All age ranges	≤1.0 mmol/L or 4.0 mg/dL ≥1.4 mmol/L or 5.6 mg/dL	CF = mg x 0.025 = mmol Based on normal range: 4.0 to 5.1 mg/dL
Total Cholesterol	All age ranges	≥6.20 mmol/L or 240 mg/dL	CF = g x 2.58 = mmol Based on normal ranges: 45 to 182 mg/dL (1-3 years), 109 to 189 mg/dL (4-6 years), 126 to 191 mg/dL (Boys 6-9 years), 122 to 209 mg/dL (Girls 6-9 years), 130 to 204 mg/dL (Boys 10-14 years), 124-217 mg/dL (Girls 10-14 years), 114 to 198 mg/dL (Boys 15-19 years), 125 to 212 mg/dL (Girls 14-19 years)
Triglycerides	All age ranges	≥4.0 mmol/L or 350 mg/dL	After >12 hours of fast) CF = g x 1.14 = mmol Based on normal ranges: 30 to 86 mg/dL (Boys 0-5 years), 32 to 99 mg/dL (Girls 0-5 years), 31-108 mg/dL (Boys 6-11 years), 35 to 114

**CRITERIA for POTENTIALLY CLINICALLY SIGNIFICANT ABNORMALITIES  
For Studies in Children**

Parameter	Age range	PCSA	Comments
			mg/dL (Girls 6-11 years), 36 to 138 mg/dL (Boys 12-15 years), 43 to 138 mg/dL (Girls 12-15 years), 40 to 163 mg/dL (Boys 16-19 years), 40-128 mg/dL (Girls 16-19 years)
Lipase	All age ranges	≥2 ULN	Based on normal ranges: 3 to 32 U/L (1-18 years)
Amylase	All age ranges	≥2 ULN	Based on normal ranges: 10 to 30 U/L (NN), 10 to 45 U/L (1-18 years)
Glucose	All age ranges	Hypoglycaemia <2.7 mmol/L or 50 mg/dL Hyperglycaemia ≥7 mmol/L or 120 mg/dL (fasted after >12 hours of fast); ≥10.0 mmol/L or 180 mg/dL (unfasted)	CF = g x 5.55 = mmol Based on normal ranges: 50 to 90 mg/dL (NN), 60 to 100 mg/dL (Child)
CRP	All age ranges	>2 ULN or >10 mg/L (if ULN not provided)	Based on normal ranges: <6 mg/L
Hematology			Common Terminology Criteria for Adverse Events v3.0 (CTCAE), 2006 ; Division of Microbiology and Infectious Diseases Pediatric Toxicity Tables, 2007 ; Division of AIDS Table for Grading the Severity of Adult and Pediatric Adverse Events, 2004; Mulberg AE et al. Pediatric Drug Development Concepts and applications. John Wiley & sons, Inc. 2009; Family Practice Notebook, LLC, 2012; Tietz NW et al. Clinical Guide to Laboratory Testing, 3 rd edition 1995
WBC	Birth/0 to 27 days old (Neonates)	<4.0 GIGA/L or 4,000 /mm  >25.0 GIGA/L or 25,000 /mm 	To be used if no differential count available
	28 days/1 month to 23 months old (Infants)	<4.0 GIGA/L or 4,000 /mm  >20.0 GIGA/L or 20,000 /mm 	
	24 months/2 years to <6 years old (Children)	<3.0 GIGA/L or 3,000 /mm  >16.0 GIGA/L or 16,000 /mm 	Based on normal ranges: 9,000 to 30,000 /mm  (birth), 9,400 to 38,000 /mm  (0-1
	6 to <12 years old (Children)	<5.0 GIGA/L or 5,000 /mm 	

**CRITERIA for POTENTIALLY CLINICALLY SIGNIFICANT ABNORMALITIES  
For Studies in Children**

Parameter	Age range	PCSA	Comments
	12 to 16/18 years old (Adolescents)	>17.0 GIGA/L or 17,000 /mm3 <4,5 GIGA/L or 5,000 /mm3 >13.5 GIGA/L or 17,000 /mm3	day), 5,000 to 21,000 /mm3 (1 day-1 month), 6,000 to 17,500 /mm3 (1 month-2 years), 5,000 to 17,000 /mm3 (2-6 years), 4,500 to 15,500 /mm3 (6-11 years), 4,500 to 13,500 /mm3 (11-18 years)
Lymphocytes (ALC)	Birth/0 to 27 days old (Neonates)	<1.2 GIGA/L or 1,200 /mm3 >17.0 GIGA/L or 17,000 /mm3	Based on normal ranges: 2,000 to 11,500 /mm3 (0-1 days), 2,000 to 17,000 /mm3 (2 days-1 month), 3,000 to 13,500 /mm3 (1 month-2 years), 1,500 to 9,500 /mm3 (2-6 years), 1,500 to 8,000 /mm3 (6-10 years), 1,200 to 5,200 /mm3 (10-18 years)
	28 days/1 month to 23 months old (Infants)	<2.0 GIGA/L or 2,000 /mm3 >13.5 GIGA/L or 13,500 /mm3	
	24 months/2 years to <6 years old (Children)	<1.0 GIGA/L or 1,000 /mm3 >9.5 GIGA/L or 9,500 /mm3	
	6 to <12 years old (Children)	<1.0 GIGA/L or 1,000 /mm3 >8.0 GIGA/L or 8,000 /mm3	
	12 to 16/18 years old (Adolescents)	<0.6 GIGA/L or 600 /mm3 >6.0 GIGA/L or 6,000 /mm3	
Absolute Neutrophil Count (ANC)	Birth/0 to 27 days old (Neonates)	<4.0 GIGA/L or 4,000 /mm3 (1 day old) <1.5 GIGA/L or 1,500 /mm3 (2-7 days old) <1.25 GIGA/L or 1,250 /mm3 (>7 day-1 month old) > 1 ULN	Based on normal ranges: 5,000 to 28,000 /mm3 (0-1 day), 1,000 to 10,000 (1 day- 1 month), 1,000 to 8,500 (1- 12 months), 1,500 to 8,500 (1 to 6 years), 1,500 to 8,000 (6 to 10 years), 1,800 to 8,000 (10 to 18 years)
	28 days/1 month to 23 months old (Infants)	<1.0 GIGA/L or 1,000/mm3 (1-3 months) <1.2 GIGA/L or 1,200 /mm3 (3-24 months) > 1 ULN	
	24 months/2 years to <6 years old (Children)	<1.2 GIGA/L or 1,200 /mm3 > 1 ULN	
	6 to <12 years old (Children)	<1.2 GIGA/L or 1,200 /mm3 > 1 ULN	
	12 to 16/18 years old (Adolescents)	<1.2 GIGA/L or 1,200 /mm3 > 1 ULN	
Eosinophils	All age ranges	>0.5 GIGA/L or 500 /mm3 Or >ULN if ULN >0.5 GIGA/L or 500 /mm3	Based on normal ranges: 0 to 500 /mm3 (0-1 month), 0 to 300 /mm3 (1 month-18 years)
Hemoglobin	Birth/0 to 27 days old (Neonates)	< 86 mmol/L or 12.0 g/dL or any decrease $\geq$ 0.31 mmol/L or 2 g/dL	CF = g x 1.55 = mmol Based on normal ranges: 15 to 20 g/dL (0-3 days), 12.5 to 18.5 g/dL (1-2 weeks), 10.0 to 13.0 g/dL (1-6 months), 10.5 to 13.0 g/dL (7 months- 2 years), 11.5 to 13.0 g/dL (2-5 years), 11.5 to 14.5 (5-8 years), 12.0 to 15.2 g/dL (13- 18 years)
	28 days/1 month to 23 months old (Infants)	< 1.40 mmol/L or 9.0 g/dL or any decrease $\geq$ 0.31 mmol/L or 2 g/dL	
	24 months/2 years to <16/18 years old (Children, Adolescents)	< 1.55 mmol/L or 10.0 g/dL or any decrease $\geq$ 0.31 mmol/L or 2 g/dL	

**CRITERIA for POTENTIALLY CLINICALLY SIGNIFICANT ABNORMALITIES  
 For Studies in Children**

Parameter	Age range	PCSA	Comments
Hematocrit	Birth/0 to 27 days old (Neonates)	< 0.39 l/l or 40 % > 0.61 l/l or 47 %	CF = % x 0.01 = l/l
	28 days/1 month to 23 months old (Infants)	< 0.29 l/l or 29 % > 0.42 l/l or 42 %	Based on normal ranges: 45 to 61 % (0-3 days), 39 to 57 % (1-2 weeks), 29 to 42 % (1-6 months), 33 to 38 % (7 months-2 years), 34 to 39 % (2-5 years), 35 to 42 % (5-8 years); 36 to 47 % (13-18 years)
	24 months/2 years to <16/18 years old (Adolescents)	< 0.32 l/l or 32 % > 0.47 l/l or 47 %	
Platelets	All age ranges	<100 GIGA/L or 100,000 /mm3 > 700 GIGA/L or 700,000 /mm3	Based on normal ranges: 250,000 to 450,000 /mm3 (NN); 300,000 to 700,000 /mm3 (1-6 months), 250,000 to 600,00 /mm3 (7 months-2 years), 250,000 to 550,000 /mm3 (2-12 years), 150,000 to 450,000 /mm3 (13-18 years)
Urinalysis			Patel HP, Pediatr Clin N Am, 2006
Ketonuria	All age ranges	Presence	Semi-quantitative methods
Glycosuria	All age ranges	Presence	Semi-quantitative methods
Hematuria	All age ranges	≥ 1+	Semi-quantitative methods
Proteinuria	All age ranges	≥ 1+	Semi-quantitative methods

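### Three rows of PCSA limits in SAP Appendix A contradict the table's own figures: WBC and creatinine at 6 to <12 years, and the adolescent WBC unit pairs

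*SAP*

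**What the plan says.** SAP Appendix A gives PCSA limits by parameter and age, often in two units, with the supporting normal ranges in the comments column.

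- **WBC, 6 to <12 years.** Low limit "<5.0 GIGA/L or 5,000" (per mm3). The high limit, ">17.0 GIGA/L or 17,000" (per mm3), falls after a page break in the text but belongs to this row, since each age row has one low and one high limit.
- **WBC, 12 to 16/18 years.** Low limit "<4,5 GIGA/L or 5,000 /mm3" (the comma is a decimal sign); high limit ">13.5 GIGA/L or 17,000" (per mm3).
- **WBC normal ranges in the same row.** "4,500 to 15,500 /mm3 (6-11 years), 4,500 to 13,500 /mm3 (11-18 years". The row carries the condition "To be used if no differential count available".
- **Creatinine, 6 to <12 years.** At or above 90 µmol/L, or 1.1 mg/dL. The comments give a conversion factor of 8.8 µmol per mg.

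SAP Section 2.1.4.4 (and protocol Section 9.3.4) has laboratory values converted to international units, which are then used throughout the listings and tables. Under the common rules of SAP Section 2.4.5, a patient with one qualifying value at any evaluation in the TEAE period enters the PCSA numerator.

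**The concern.** A PCSA limit should be a single number whatever the unit, and a low limit should not lie above the lower limit of normal that the same table quotes. Three rows fail one of these tests. If a limit is programmed as printed, a child with a normal value may be counted as abnormal. If two programmers take different units, they will get different counts. PCSA status also sorts patients by baseline category (SAP Section 2.4.5.3), so a misplaced limit can affect that split as well.

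**Working it through.** **Inputs.** All limits, normal ranges and the creatinine factor come from SAP Appendix A. The rule on units is in SAP Section 2.1.4.4.

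**Conversions.** WBC: Giga/L × 1,000 = /mm3. Creatinine: mg/dL × 10 = mg/L, and mg/L × 8.8 = µmol/L, so mg/dL × 88 = µmol/L.

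**Pairs that reproduce.**
- WBC, 6 to <12 years: 5.0 × 1,000 = 5,000 and 17.0 × 1,000 = 17,000. Both agree.
- Creatinine, under 6 years: 0.6 × 88 = 52.8 against 53 printed. Agrees after rounding.
- Creatinine, 12 to 16/18 years: 1.5 × 88 = 132.0 against 132 printed. Agrees.

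**Pairs that do not.**

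| Row | First unit | Converts to | Printed | Gap |
|---|---|---|---|---|
| WBC low, 12 to 16/18 y | 4.5 Giga/L | 4,500/mm3 | 5,000/mm3 | 500 (5.0/4.5 = 1.11) |
| WBC high, 12 to 16/18 y | 13.5 Giga/L | 13,500/mm3 | 17,000/mm3 | 3,500 (17.0/13.5 = 1.26) |
| Creatinine, 6 to <12 y | 1.1 mg/dL | 96.8 µmol/L | 90 µmol/L | 6.8 (96.8/90 = 1.076) |

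The printed adolescent /mm3 figures are the same as those of the 6 to <12 row. The adolescent Giga/L figures equal the quoted 11-18 year normal range, 4.5 to 13.5. In the other direction, 90/88 = 1.02 mg/dL. A creatinine of 90 to <96.8 µmol/L is therefore a PCSA if judged in µmol/L and not if judged in mg/dL.

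**WBC low limit against normal, 6 to <12 years.** The row quotes "4,500 to 15,500 /mm3 (6-11 years", a lower limit of 4.5 Giga/L. The PCSA limit is <5.0, so 4.5 to <5.0 is normal by the table and also a low PCSA. Because this pair agrees between units, choosing a unit does not remove the conflict. The normal-range labels overlap at their ends. At age 11 both candidate ranges start at 4.5. At age 6 the 2-6 year range (5,000 to 17,000) could also be read, but at ages 7 to 11 it cannot.

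The other low limits in the row do not behave this way: infants <4.0 against 6.0, ages 2 to <6 <3.0 against 5.0, adolescents 4.5 against 4.5.

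**Possible weight of one flag.** Protocol Section 6.1.1 plans 6 patients per weight group and regimen, so about 12 on a non-selected regimen. One flag is 1/12 = 8.3% if all 12 are in the denominator. The documents do not say how many blood counts will lack a differential, so the expected number of flags cannot be calculated.

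**The case against.** The strongest reply is that little of this reaches a table, and most of that reply stands.

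- **Units.** Appendix A joins its pairs with a bare or. Section 2.1.4.4 nevertheless settles the choice: international units govern, and only lipids are also shown in US units. Adolescent WBC is then judged at 4.5 and 13.5, and creatinine at 90 µmol/L. This disposes of the adolescent WBC effect. It does not touch the WBC low limit at 6 to <12 years, and it does not show which creatinine value was intended.
- **Differential.** The hematology panel includes a differential (protocol Section 9.3.4), so the WBC row should seldom be used. This stands.
- **Coincidence with the 2-6 year range.** The 5.0 and 17.0 limits match that range, but this does not prove that they were carried over. The table's own limits for 2 to <6 years are 3.0 and 16.0, so the row does not follow the quoted ranges mechanically. The conflict with 4.5 does not depend on how it arose.

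Four stronger readings are tempting and are not supported.

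- A reader might infer that high counts of 15.5 to 17.0 are missed at 6 to <12 years. A PCSA high limit may lie above normal: the same table uses 3 × ULN for ALT and >700 Giga/L for platelets, against a quoted 550 for ages 2-12. Values above normal still appear in the normal-range shift tables and flagged listings of SAP Section 2.4.5.3.
- A reader might take these for alert limits that drive care. They are tabulation criteria; guidance on following up laboratory abnormalities is in protocol Appendix G.
- A reader might think the leukopenia signal is weakened. It is covered separately by the ANC PCSA limit, the graded neutropenia and lymphopenia summaries, and the leukopenia category in SAP Table 5.
- A reader might extend the creatinine point to adolescents, or object that 90 µmol/L lies within the quoted normal range. The adolescent pair agrees exactly. The quoted range, "0.5 to 1.5 mg/dL (1 to 16/18 years", pools all those ages, so a lower limit for younger children is not in itself an error.

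**Conclusion.** The table needs correcting in three rows, and the consequences are minor.

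1. WBC, 6 to <12 years: the low limit counts normal values of 4.5 to <5.0 Giga/L as PCSAs in either unit, only where no differential is available. This is the one definite conflict between a limit and the normal range for its age.
2. WBC, 12 to 16/18 years: the unit pairs are wrong by 500 and 3,500/mm3. No effect on results is expected, provided that Section 2.1.4.4 is followed.
3. Creatinine, 6 to <12 years: the two limits differ by 7.6%, and values of 90 to <96.8 µmol/L qualify in one unit only. Under the SI rule 90 applies, but the documents do not show whether 90 or 96.8 was meant.

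This rests on assigning the >17.0 line to the 6 to <12 row (only the remarks on the high limit depend on that), and on reading 6-year-olds under the 6-11 year range. The PK endpoint, efficacy and patient management are unaffected.

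**What to change.** In SAP Appendix A:

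- Reconcile the WBC low limit for 6 to <12 years with the quoted 6-11 year range, so that it is not above 4.5 Giga/L (4,500/mm3). The high limit can stay.
- Change the adolescent WBC /mm3 figures to 4,500 and 13,500.
- Have the sponsor confirm which creatinine value is intended for 6 to <12 years, and make the two units equal under the table's factor.
- Add a note that the SI value governs, with a reference to SAP Section 2.1.4.4.

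The cost is three table rows and one note, with a matching check of the PCSA program. No data collection changes.

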## Appendix B Visit Windows Based on Day Ranges for Laboratory values, Vital Signs, ADA, and PK measurements

Measurements of PK and ADA will be mapped to each visit/time point based on [Table 1](#); Labs and vital signs will be mapped to each visit/time point based on [Table 2](#). Below are the rules for the lab tests that are not included in [Table 2](#):

- Pregnancy test results will be summarized at baseline and post-treatment, where the baseline will be defined based on all the pregnancy tests (serum and urine) performed prior to the first IMP; and post-treatment value will be based on all the pregnancy tests performed post first IMP. The value is positive if at least one of the tests is positive.
- Rheumatoid factor (RF) and Urinalysis will only be measured during the screening period. Only the value at baseline will be summarized.

